## Risks of Echocardiography

This is a noninvasive procedure. There is no known risk associated with this procedure. Gel will be applied during the test which may cause coldness and/or irritation.

#### Risks of Accelerometer Use

Common risks associated with wearing the accelerometer are redness, irritation, and chaffing.

#### Risks of Right heart Catheterization

Common risks: pain at the needle entry site and slight risk of bleeding around the site, bruising at site, lightheadedness or dizziness during the needle stick.

Infrequent risks: puncturing the lung which would require a chest tube insertion, irregular heartbeats which usually stop when the long tube is removed from the heart.

Very rare complications include cardiac arrhythmias, cardiac tamponade, low blood pressure, infection, or embolism caused by blood clots at the tip of the catheter.

## Risks of the Use of Micromanometer Catheter during Catheterization

The micromanometer pressure and flow catheters are FDA approved, and have been used for clinical/investigative indications for over 25 years. Moreover, these catheters do not pose any inherent risk to patients. The catheter will be placed through the clinical Swann-Ganz catheter that is within the preexisting jugular venous sheath. This obviates the need for an additional venipuncture. This catheter has successfully been used without complications by the study Principal Investigator for the past 5+ years. Risks associated with this procedure are estimated to be rare, which include abnormal heart rhythm, bleeding, or perforation of the heart or pulmonary artery.

## Risks of Medications used during Catheterization

The medications used for sedation are relatively brief in duration and should wear off within several hours. The side effects are listed below for each drug.

- 1% Lidocaine: will be used to numb the area prior to the insertion of the cardiac catheter into either the arm, neck or groin vein. A common side effect is slight burning at the site which dissipates quickly.
- Fentanyl: Common side effects include temporary light-headedness, dizziness, and nausea, vomiting or sweating.
- Midazolam: Common side effect includes drowsiness. Infrequent side effects are nausea, vomiting. Breathing problems are rare. Allergic reactions (e.g., hives, itching, etc.) to lidocaine, fentanyl, or midazolam are rare.

## Risks of Fluoroscopy during the Catheterization

An x-ray may be done, if indicated, on participants whose neck vein is used for the catheterization. An X-ray performed for the purpose of this research study involves exposure to radiation. Each x-ray will result in a radiation dose of approximately 3 rems to the neck with minimal exposure of other body areas. A total of 9 rems if all three RHC's are performed. For comparison, radiation workers are permitted, by Federal regulation, to receive a maximum annual radiation dose of 20 rems to the most sensitive organs of their body. There is no minimum amount of radiation exposure that is recognized as being totally free of the risk of causing genetic mutations (abnormal cells) or cancer. However, the risk associated with the

amount of radiation exposure received from participation in this study is considered to be low and comparable to everyday risks.

## Risks of Cardiopulmonary Exercise Test (CPET)

CPET is a well-established clinical tool. The risk of serious or fatal complications is rare. The risks include but are not limited to the following:

- Common risks include shortness of breath, mild angina, musculoskeletal discomfort.
- Infrequent risk includes hypotension, chest pain.
- Rarely, exercise may cause moderate to extreme pain which could be due to muscle sprains, muscle strains, broken bones, or chest pain, changes include shortness of breath, abnormal blood pressure, or fainting, myocardial infarction, prolonged cardiac arrhythmia, stroke, or sudden death are rare (occur in <1% of people).

#### Risk of Spirometry

Spirometry infrequently can make the chest tight or lead to shortness of breath. Albuterol will be available if this occurs. Rarely, a subject may have coughing or lightheadedness with spirometry. If Albuterol is given, the subject will get up to 4 puffs of albuterol with these tests. Albuterol may make a subject feel slightly jittery or nervous, but the feelings are temporary.

## Risks of Intravenous Glucose Tolerance Test (IVGTT)

- IV Catheter Insertion Common Risks: bruising, soreness, phlebitis. Infrequent Risks: infiltration (a leakage of anything that has been given through the vein (such as the saline, dextrose, deuterated glucose, insulin) into the arm tissue that surrounds the vein and holds the IV). Other Risks: infection, dizziness/fainting, bleeding.
- IVGTT Common Risks: (occurring in less than 25% of people) include: phlebitis (inflammation of a vein), transient hyperglycemia (high blood sugar not requiring treatment). Rare side effects (occurring in less than 1% of people) include: Hypoglycemia (low blood sugar) which may cause symptoms such as shakiness, nervousness, sweatiness, hunger, dizziness, or fast heart rate. If severe, hypoglycemia can cause coma, seizure, or even death.

#### Reproductive Risks

It is not known if the study drug can affect an unborn baby. Therefore, subjects should not become pregnant or father a baby while on this study. If subjects are physically able to father a baby, subjects must use an effective method of birth control while on this study. If subjects become aware that they or their sexual partner is pregnant during the course of their participation in this research study, subjects must contact, as soon as possible, the study investigator.

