## 2.4.6 Laboratory Testing

The following peripheral blood samples will be evaluated at the screening/baseline, week 10, cross-over, and end of treatment visits for follow-up comparison purposes: fasting glucose, comprehensive metabolic panel, hemoglobin A1C, fasting lipid profile, PT/PTT, complete blood count, platelet and differential, NT-proBNP, and research blood samples for plasma

nitrite concentrations, red cell iron-nitrosyl-hemoglobin, and platelet studies. Urine pregnancy test will be performed on females of child-bearing potential at baseline, week 10, cross-over visit, and at the end of study treatment. The samples will be collected and analyzed at the UPMC Presbyterian laboratories. The NT-proBNP blood sample will be sent to the Translational Research Core Laboratory (TRCL) for storage and analysis. Research samples will be sent to [name]/[name] labs in Vascular Medicine Institute (VMI) for storage and analysis.

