#### 3.1.1 Inclusion of Women and Minorities

Both men and women of all races and ethnic groups are eligible for this trial. Women who meet the inclusion criteria, and have none of the exclusion criteria, will be enrolled without restriction as dictated by the study protocol. Because of the use of a study medication, woman of child bearing potential must meet specialized inclusion/exclusion criteria to minimize this risk.

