#### 3.3 EXCLUSION CRITERIA

Subjects meeting any of the exclusion criteria at baseline will be excluded from participating in study.

- Age less than 18 years
- SBP > 170 or < 110 mmHg
- DBP > 95 or < 60 mmHg
- Hemoglobin A1C > 10
- Positive urine pregnancy test or breastfeeding
- Ejection Fraction < 40%
- Dementia
- End-stage malignancy
- Major cardiovascular event or procedure within 6 weeks prior to enrollment
- Severe valvular disease
- Known chronic psychiatric or medical conditions that may increase the risk associated with study participation in the judgement of the investigator would make the subject inappropriate for entry into this study
- Smoker
- Hemoglobin < 9 g/dL
- Serum creatinine > 3.0 mg/dL
- Recent (<3 months) addition or change in dosing of hormonal contraceptive medications (OCP, IUD, DepoProvera)
- Receipt of an investigational product or device, or participation in a drug research study within a period of 15 days;
- RHC < 2 weeks from study screening RHC unless clinically indicated

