A recent study determined the safety and feasibility of prolonged intravenous nitrite infusion. Twelve adult volunteers received increasing starting doses of sodium nitrite, 4.2 to 533.8 µg/kg/hr for 48 hours. Dose limiting toxicity occurred at 445.7 µg/kg/hr (10.6 mg/kg/day) and was limited to asymptomatic transient decreases of arterial blood pressure of up to 20 mmHg and asymptomatic increases of methemoglobin levels above 5%. No tolerance or clinically significant rebound was observed. Note, this is 8.2 times the daily dose we plan to use in this trial (based on an adult body weight of 95 kg).

For nitrite, two retrospective case-control studies have shown that high maternal dietary nitrite intake from cured meat or drinking water during pregnancy might be associated with risk of childhood brain tumors and possibly gastric and esophageal cancer. This evidence is only based on retrospective case-control studies; cohort studies have found no significantly increased risks.

In the 2001 National Toxicology Program (NTP) Report summarizing 2-year rodent drinking water studies, there was no evidence of carcinogenic activity of sodium nitrite in male or

female F344/N rats exposed to up to 130 mg/kg/day in males and 150 mg/kg/day in females, or in male B6C3F1 mice exposed to up to 220 mg/kg/day. There was equivocal evidence of carcinogenic activity of sodium nitrite in the highest dose of 165 mg/kg/day in female B6C3F1 mice based on the positive trend in the incidences of squamous cell papilloma or carcinoma (combined) of the forestomach. Exposure to sodium nitrite in drinking water resulted in increased incidences of epithelial hyperplasia in the forestomach. However, no chromosomal damage (genetic toxicity) was observed in three studies conducted in rats and mice *in vivo*. Taken together, these findings suggest minimal carcinogenic nitrite-mediated risk.

In the current study, we will use lower doses of nitrite than used safely in any of these studies. Our nitrite dose of 40 mg three times daily is lower than the dose used on the cardiovascular IND and < 40% of the dose for cyanide poisoning.

To summarize, we anticipate the following symptoms by organ system and likely frequency of risk:

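### The protocol's only mandatory birth-control rule covers subjects who can father a baby; no matching rule covers women of child-bearing potential

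*Combined protocol and SAP*

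**What the plan says.** Section 5.2, Reproductive Risks, begins from uncertainty: "It is not known if the study drug can affect an unborn baby". It draws the consequence for both sexes in advisory terms: "subjects should not become pregnant or father a baby while on this study". It then makes contraception compulsory for one group: "If subjects are physically able to father a baby, subjects must use an effective method of birth control while on this study". It closes by requiring any subject who learns of a pregnancy, their own or a partner's, to tell the investigator as soon as possible.

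Section 3.1.1 says that, because a study drug is used, "woman of child bearing potential must meet specialized inclusion/exclusion criteria to minimize this risk". Two exclusion criteria in 3.3, repeated in the synopsis, bear on this. One is "Positive urine pregnancy test or breastfeeding". The other bars anyone who started a hormonal contraceptive, or changed its dose, within the previous 3 months.

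Under 2.4.6, urine pregnancy tests are "performed on females of child-bearing potential at baseline, week 10, cross-over visit, and at the end of study treatment". Table 1 places the first of these at screening. Section 2.7 lists pregnancy as a ground for withdrawal, and the Stopping Rule in 5.5.2 discontinues any participant with a positive test.

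**The concern.** The hazard that 5.2 names is to an unborn baby, and the person who would carry an exposed pregnancy is a woman taking nitrite. Yet the one sentence that says *must* does not reach her. As written, a fertile woman who uses no contraception can satisfy every eligibility criterion and take the drug without breaching any contraceptive requirement. The protocol gives no reason for treating the sexes differently.

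What is at stake is participant safety. The primary endpoint, the sample size and the analysis are untouched.

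**Working it through.** No arithmetic beyond counting applies. The check is whether any other part of the document supplies the missing obligation.

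**Criteria.** Section 3.2 has 3 inclusion criteria and 3.3 has 17 exclusions: 3 + 17 = 20. Criteria that require contraception: 0. Two relate specifically to women: pregnancy or breastfeeding, and recent hormonal-contraceptive change. Both describe status at entry. The second restricts who may join; it does not oblige anyone to use a method. The synopsis lists are the same in this respect.

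**Mandatory birth-control sentences.** One in the whole document, in 5.2. Sentences that cover women: 0.

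**Other controls, side by side.**

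| Where | What it does | Requires contraception in women? |
|---|---|---|
| 5.2, general sentence | Advises both sexes against pregnancy or fathering a baby | No: states an outcome, names no method |
| 3.1.1 | Promises special criteria for women of child-bearing potential | No: 3.2/3.3 deliver entry status only |
| 3.3 and synopsis | Exclude pregnancy, breastfeeding and recent hormonal change | No |
| 2.4.6 and Table 1 | Urine tests at screening/baseline, week 10, cross-over and end of treatment | No: detection |
| 2.2 and 2.2.3 | Dosing and symptom diary; weekly calls while on treatment | No: occasions for a pregnancy to come to light |
| 5.2, last sentence | Requires a pregnancy to be reported | No: acts afterwards |
| 2.7 and 5.5.2 | Withdrawal or discontinuation | No: acts afterwards |

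**Internal comparison.** The advisory sentence in 5.2 covers fathering a baby as well as becoming pregnant. The protocol still added a compulsory sentence for subjects who can father a baby, so it did not treat the advice as sufficient for them. The same reasoning applies at least as strongly to subjects who can become pregnant.

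**Open label.** Sections 2.2.2 and 2.3.5 offer 6 further months of nitrite after the end-of-treatment visit. The in-person visits at months 3 and 6 list questionnaires, a walk test and NT-proBNP. Scheduled pregnancy tests: 4 up to end of treatment (1 + 1 + 1 + 1) and 0 afterwards.

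**The case against.** The best reply is that this is a slip of the pen with little consequence. The sentences on either side of the quoted one speak to both sexes, so the aim of avoiding pregnancy in women is plain. Pregnancy bars entry, must be reported and ends participation. Weekly calls and a diary give regular chances for it to surface. The consent form, a natural place for contraception instructions, is not in the public copy. Recruitment draws partly on a geriatric centre and an older-adult registry (4.1), so few or no fertile women may enrol.

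Most of this stands, and it limits the size of the point. It does not supply the missing obligation. Eligibility starts at 18 with no upper age or menopausal limit, and the protocol's own pregnancy tests and hormonal exclusion show that it expects such women.

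A reader might infer more than the documents support:

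- *That the sponsor chose to exempt women.* Nothing says so, and the neighbouring sentences point the other way.
- *That a fetus could be exposed unnoticed for about 10 weeks, the spacing of tests within a treatment period.* That is a worst case in which every weekly call, the diary and the woman's own reporting all fail. It is not an expected exposure.
- *That the dietary-nitrite tumour reports in 5.1 make the gap grave.* Those case-control findings concern cured meat and drinking water. The same paragraph adds that "cohort studies have found no significantly increased risks", and the section goes on to judge the carcinogenic risk minimal. The statement in 5.2 that the fetal effect is unknown is enough to justify the rule.

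**Conclusion.** The gap in the text is real and minor. One safety rule omits the group most directly concerned, and neither the 20 criteria nor the promise in 3.1.1 makes up for it. The existing controls screen, detect and respond; none requires prevention.

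Confidence is high for the wording and low for the practical effect. The ceiling is the 26 planned subjects. The number affected is unknown and may be zero. The conclusion assumes that *should not become pregnant* does not amount to a contraceptive requirement, and it is confined to the protocol text. A reader should not infer that women in the trial were in fact left without contraceptive instruction: the consent form may have given it. If it did, the protocol should still be aligned, because eligibility is judged against 3.2 and 3.3.

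**What to change.** In 5.2, reword the sentence so that subjects able to become pregnant or to father a baby must use an effective method of birth control for the whole time on study drug, including the open-label period. Keep the washout covered, as the present wording does. Add one matching criterion to 3.2/3.3 and to the synopsis. The sponsor and IRB choose the acceptable methods. These must fit the hormonal exclusion in 3.3: a hormonal method unchanged for at least 3 months, or a non-hormonal one.

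Secondary and optional: list a urine pregnancy test for women of child-bearing potential at the existing month 3 and month 6 open-label visits. A woman who completes open label would then have 4 + 2 = 6 scheduled tests. This extends detection into open label. It does not replace the contraception rule and does not alter test spacing in the blinded periods.

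The cost is one sentence and one criterion line, repeated in the synopsis. The optional part adds a schedule footnote and at most 2 urine tests per woman concerned, at visits that already exist. A very small loss of candidates is possible, and a woman who starts a hormonal method in order to comply would wait 3 months before entry.

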#### Risk of Collection and Storage of Private Health Information and Internet Usage

Although we are taking many steps to protect the participants' information, there is always a chance that their information or identity could be disclosed. We will continue to review and improve the ways we keep their information private. To protect their information, paper-based records will be kept in a secure location and only be accessible to personnel involved in the study. Paper charts will contain subject identifiers but will be in locked cabinets within a locked office on a unit that has restricted access.

#### **5.3 ALTERNATIVE TREATMENTS**

The alternative treatment for the subjects participating in this investigation is to continue their medical care under the direction of their primary physicians.

#### **5.4 POTENTIAL BENEFITS**

Participation in the proposed research may or may not provide a direct benefit to participants in this research. This research involves interventions and/or procedures that present greater than minimal risk to the involved adults, but which holds out the potential for direct individual benefit. The risk is justified by the extent of potential benefit to the involved adults, which includes possibly revealing previously-undiagnosed morbidities commonly seen in obesity such as hyperlipidemia, impaired fasting glucose, or type 2 diabetes mellitus. Information obtained from the proposed research will provide information about the relationship between metabolic syndrome and PH-HFpEF and patient outcome.

Based on the preceding assessment of risks and potential benefits, the risks to subjects are reasonable in relation to anticipated benefits. The research presents a balance of risks and expected direct benefits similar to that available in the clinical setting.

#### 5.5 DATA SAFETY MONITORING PLAN

## 5.5.1 Data Safety Monitoring Board

A Data and Safety Monitoring Board (iDSMB) independent of the study investigators will monitor this clinical trial for additional measure of subject protection. The iDSMB consists of clinicians completely independent of the investigators who have no financial, scientific, or other conflict of interest with the trial.

The iDSMB will conduct interim monitoring of accumulating data from research activities to assure the continued safety of human subjects, relevance and appropriateness of the study, and the integrity of research data.

## 5.5.2 Data Safety Monitoring Plan

Assuring patient safety is an essential component of this protocol. The study Principal Investigator has primary responsibility for the oversight of the data and safety monitoring. The study investigators will evaluate all adverse events. All subjects who have AEs, whether considered associated with the use of the study medication or not, must be monitored to determine the outcome. The clinical course of the AE will be followed up according to accepted standards of medical practice, even after the end of the period of observation, until a satisfactory explanation is found or the Principal Investigator considers it medically justifiable to terminate follow-up.

All untoward medical occurrences observed in subjects receiving the study drug will be recorded on the participants' adverse event worksheets by the study coordinator under the supervision of the principal investigator. The worksheets will then be reviewed for completeness and internal consistency. In addition to internal safeguards built into a computerized system, external safeguards will be put in place to ensure that access to the computerized system and to the data is restricted to authorized personnel. Training conducted by qualified individuals on a continuing basis will be provided to individuals in the specific

operations with regard to computerized systems that they are to utilitze during the course of the study.

The Sponsor and Investigator will prepare a detailed written summary of serious, unexpected, and treatment-related adverse events, and will compare and contrast each event with prior events. The written summary will be provided to the DSMB and the IRB.

In addition, the DSMB Report addressing the following information will be submitted to the IRB at the time of continuing review, annually or more often as required:

- A list of the research personnel who participated in the data and safety monitoring.
- The frequency of monitoring that took place during the renewal intervals and/or the dates that data and safety monitoring was conducted.
- A summary of cumulative data related to unanticipated problems (including adverse events) including a determination of causality and whether the risk to benefit assessment has changed.
- If appropriate, a summary of pertinent scientific literature reports, therapeutic developments, or results of related studies that may have an impact on the safety of study participants or the ethics of the research study.
- A summary of the outcome of reviews conducted to ensure subject privacy and research data confidentiality.
- Final conclusions regarding changes to the anticipated benefit-to-risk assessment of the study participation and final recommendations related to continuing, changing, or terminating the study.

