## Neurologic

Common: noneFrequent: none

Rare: headache, dizziness, seizure, coma

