## 5.5.4 Frequency of Monitoring

The Investigator will review subject safety data as it is generated. The Investigator and the research staff will meet at approximately monthly intervals to re-evaluate study goals, subject recruitment, data coding and retention, documentation and identification of adverse events, complaints, and confidentiality of subjects. There will be an evaluation of the progress of the research study, including assessments of data quality, time lines, participant recruitment, accrual, and retention. The Investigator will also review the outcome and adverse event data to determine whether there is any change to the anticipated benefit-to-risk ratio of study participation and whether the study should continue as originally designed or should be reevaluated and changed.

The DSMB will also be expected to meet as needed, but not less than every six months to provide an overall summary status report to the regulatory agencies.

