## **5.5.6 Adverse Events Reporting Timeline**

Life-threatening or fatal unexpected adverse events associated with the use of the study drug

or procedures must be reported to the DSMB and the IRB within 24 hours of discovery of the incident with subsequent follow-up submission of a detailed written report.

The FDA must be notified by telephone or facsimile transmission of a human adverse event that is fatal or life-threatening no later than 7 calendar days after receiving the respective human adverse event information, followed by the subsequent submission of a written IND Safety Report.

Serious and unexpected adverse events associated with the use of the study drug or procedures must be reported to the DSMB and the IRB with subsequent follow-up submission of a detailed written report in accordance with the respective policies and procedures of the IRB. Written IND Safety Reports will be submitted to the FDA as soon as possible and, in no event, later than 15 calendar days following the investigator-sponsor's receipt of the respective adverse event information.

A summary report of the DSMB's findings will be prepared and submitted to the regulatory agencies.

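### Outside the methemoglobin and blood-pressure stopping rule, a serious event judged expected has no prompt route to the DSMB

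*Combined protocol and SAP*

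**What the plan says.** Section 5.5.2 has the sponsor and investigator prepare "a detailed written summary of serious, unexpected, and treatment-related adverse events", and adds: "The written summary will be provided to the DSMB and the IRB". It gives no deadline.

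Section 5.5.6 sets two DSMB duties. The first covers "Life-threatening or fatal unexpected adverse events associated with the use of the study drug" or procedures, which "must be reported to the DSMB and the IRB within 24 hours of discovery". The second covers other events that are both serious and unexpected and are associated with the drug or procedures; its timing follows IRB policy. A separate sentence requires the FDA to be told of a fatal or life-threatening event within 7 calendar days and does not mention expectedness.

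Section 5.5.5 counts an event as serious only if the investigator also thinks it study-related.

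The risk text in 5.1 closes with a list introduced by "To summarize, we anticipate the following symptoms by organ system and likely frequency of risk". Its entries include "Rare: headache, dizziness, seizure, coma", and under other organ systems methemoglobinemia, hypotension and cyanosis. Section 5.2 lists procedure risks: for the exercise test, "myocardial infarction, prolonged cardiac arrhythmia, stroke, or sudden death are rare"; for right heart catheterisation (RHC), tamponade and embolism; for the micromanometer, perforation of the heart or pulmonary artery; and for the glucose tolerance test (IVGTT), hypoglycemia severe enough to cause coma or death.

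On meetings, section 5.5.4 says: "The DSMB will also be expected to meet as needed, but not less than every six months".

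**The concern.** A DSMB in a small trial with repeated invasive and exercise testing is there largely to watch for harms that can be foreseen. Expectedness is a sensible filter for regulatory safety reports, where the aim is to flag what is new about a drug. It suits a DSMB poorly, because a foreseen harm that occurs, or recurs, is what may change the balance of benefit and risk. If expectedness controls what the DSMB is told promptly, and the protocol's own risk sections can be used to decide it, a life-threatening event at a research procedure could stay outside the prompt reporting route while subjects continue to undergo the same procedure.

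**Working it through.** No stated figure is at issue, so the check sets every route to the DSMB side by side.

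| Route | Events covered | Must be unexpected? | Timing |
|---|---|---|---|
| 5.5.2 written summary | Serious, treatment-related | Yes, on the natural reading | None stated |
| 5.5.6, first duty | Fatal or life-threatening, associated with drug or procedures | Yes | 24 hours |
| 5.5.6, second duty | Serious, associated with drug or procedures | Yes | IRB policy |
| 5.5.2 Stopping Rule, enrolment suspended | Methemoglobin above 5% or the listed blood-pressure events, in two subjects despite dose reduction | No | On trigger |
| 5.5.2 Stopping Rule, study halted | A fatal event, or a listed event that is life-threatening despite dose reduction | Fatal event: yes. Listed event: no | On trigger |
| 5.5.1, 5.5.4, 5.6.2 general monitoring | Accumulating data | No | As needed, at least six-monthly; no data flow given |

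**Does the filter bite?** The protocol neither defines the term nor names a reference list. The only text an investigator could judge expectedness against is 5.1 and 5.2.

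**Tracing one case.** Take a tamponade at the week 10 RHC. It is life-threatening and procedure-related. Judged unexpected, it goes to the DSMB within 24 hours. Judged expected because 5.2 lists it, it meets neither duty in 5.5.6, nor the 5.5.2 summary on its natural reading, and it is not one of the events named in the Stopping Rule. Only general monitoring remains. The FDA sentence would still apply. Perforation, infarction or stroke at a study procedure follows the same path. So does an expected death, because the fatal-event halt also requires the event to be unexpected.

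**Exposure.** Each subject who completes has RHC at week 10 and at end of treatment, so 2 × 26 = 52. With a screening RHC in everyone it is 3 × 26 = 78, not counting screen failures.

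**Meeting interval.** Six months = 365.25 / 2 / 7 = 26.1 weeks, against 22 weeks for a subject's course. A whole course can fall between two scheduled meetings.

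**How far a two-subject trigger helps.** The documents give only words such as rare, or below 1%, so the per-subject risk p is an assumption. With n = 26:

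- P(at least 1) = 1 − (1 − p)^26
- P(at least 2) = 1 − (1 − p)^26 − 26p(1 − p)^25

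At p = 1%: 1 − 0.770 = 23.0%, and 23.0% − 20.2% = 2.8%.

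| Assumed p | At least 1 of 26 | At least 2 of 26 |
|---|---|---|
| 0.5% | 12.2% | 0.8% |
| 1% | 23.0% | 2.8% |
| 2% | 40.9% | 9.5% |
| 5% | 73.6% | 37.6% |
| 10% | 93.5% | 74.9% |

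For a rare harm, a single case is much likelier than the pair needed to suspend enrolment. This flatters the Stopping Rule, which also requires dose reduction first and names no procedure harm.

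**The case against.** The strongest reply is that the protocol has more oversight than the two reporting sections suggest, and much of that stands.

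- **The Stopping Rule.** A reader might infer that the main nitrite harms have no event-level route to the DSMB. They do: methemoglobin and blood-pressure events reach it without any test of expectedness. The route is narrow, but it exists.
- **Listed does not mean expected.** Nothing ties the term to 5.1 or 5.2. Only 5.1 speaks of anticipating events; 5.2 lists risks, many of them rare. Coma on nitrite is a weak example: 5.1 links coma to methemoglobin above 50% and reports levels never above 3% at doses below 75 mg, so an investigator could readily call it unexpected. What remains is that the investigator could decide either way, and the protocol gives no rule.
- **The wording of the summary.** The three adjectives in 5.5.2 could mean three separate categories. The paired wording in 5.5.6 favours the cumulative reading. On the broader reading the summary still has no deadline.
- **Comparison with earlier events.** A reader might take 5.5.2 to mean that the DSMB compares events only with earlier unexpected ones. It does not say that: the sponsor and investigator make the comparison, and the earlier events are not restricted.
- **General monitoring.** Section 5.5.3 puts adverse events under review separately from unanticipated problems, 5.5.1 and 5.6.2 promise interim and continuous monitoring, and the DSMB can meet as needed. None of these says who tells the DSMB that an expected serious event has occurred.

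**Conclusion.** The point holds in limited form. Apart from the Stopping Rule, the protocol requires no prompt DSMB notice of a serious event judged expected, and it leaves that judgement undefined. The clearest gap is for listed procedure harms, such as tamponade, perforation, infarction and stroke, which have no prompt route if so judged. This rests on the cumulative reading of the 5.5.2 summary and on an investigator using the risk sections to decide expectedness; the documents allow that but do not require it.

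The size should not be overstated. One might infer that notice slips from 24 hours to six months for every such event. The documents do not support that: the 24-hour clock applies only to fatal or life-threatening events, other serious events have no fixed clock to lose, and six months is the longest scheduled interval, not the expected delay. Few events are likely to be affected in 26 subjects, but any one of them could matter to whether the procedures continue unchanged.

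Two further features support a change. The FDA sentence has no expectedness filter, so the FDA could be told of an event that the trial's own board need not be told of. And 5.5.5 narrows the flow at its source, because an event the investigator considers unrelated is never a serious adverse event under this protocol.

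**What to change.** Four wording changes, with the Stopping Rule and clinical management left as they are:

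1. **5.5.6:** delete *unexpected* from the sentences on notifying the DSMB. Fatal or life-threatening events associated with the drug or procedures then go to it within 24 hours whether or not they were foreseen.
2. **5.5.2:** give the DSMB a listing of all serious adverse events by treatment period, regardless of expectedness or judged relatedness.
3. **5.5.5:** remove from the definition of a serious adverse event the condition that the investigator thinks it study-related. Without this the listing in item 2 would be incomplete. Relatedness can still be recorded for each event.
4. **5.5.6:** keep *unexpected* for written IND safety reports only, and define it against a named reference list.

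The cost is a protocol amendment and a few more DSMB notices, some for background disease. For a listed harm at an assumed per-subject risk of 1% to 5%, the expected number of affected subjects is 26 × 0.01 = 0.26 to 26 × 0.05 = 1.3. The documents give no rate for serious events from background disease, so the added lines in the listing cannot be estimated, but with 26 subjects at one centre they should be manageable.
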